There is extensive preclinical and clinical data on this agent, which is FDA approved in adults with recurrent multiple myeloma at a dose of 20mg 3x/week x 2 weeks of a 3 week cycle⁷⁰.

In the present trial, we seek to evaluate this promising drug for use as a single agent in children with recurrent/progressive DIPG. The initial dose level we propose to use is approximately 80%

of the approved adult dose.

Rationale for Amendment 4:

We have enrolled 11 patients to date, 7 so far are evaluable (1 was inevaluable and 3 are still in the DLT period). Two patients enrolled onto dose level 1 and did not experience a DLT. The subsequent 6 patients were enrolled onto dose level 2. One patient experienced a dose limiting toxicity of grade 3 thrombocytopenia, and was dose reduced to level 1. One patient was inevaluable due to disease progression. A second patient experienced dose limiting toxicities of grade 4 thrombocytopenia and grade 4 neutropenia, and was dose reduced to level 1. Given 2 occurrences of DLTs at dose level 2, the subsequent 3 patients have been enrolled onto dose level 1. Should they tolerate dose level 1 (10mg/m²), it will be declared the maximum tolerated dose (MTD) for the 3 weeks on 1 week off schedule.

The recommended phase 2 dose has been identified for children with recurrent/progressive DIPG as 10 mg/m², and now we will evaluate panobinostat as a single agent in children with DIPG who have not yet progressed in a separate stratum (Stratum 2), using an alternative schedule. Given the limited BBB (blood brain barrier) penetration of panobinostat, it is highly desirable to maximize the dose administered as part of treatment. To improve the tolerability of panobinostat, we propose a new schedule of Monday, Wednesday, Friday dosing every other week. *In vivo* DIPG orthotopic xenograft data show prolonged duration of tumor suppression in mice treated with weekly 20mg/kg systemic panobinostat compared to mice treated 10mg/kg 3 times per week ⁵⁴, suggesting that higher doses administered less frequently may be more beneficial than lower doses administered more frequently. In addition to the change in dosing schedule, we will be studying DIPG patients prior to progression to avoid confusion between effects of tumor progression and putative toxicity of the agent. Furthermore, our plans for future efficacy studies focus on DIPG patients prior to progression in order to maximize the likelihood of success.

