5.1.3 Dose-Limiting Toxicity

Management and dose modifications associated with adverse events are outlined in Section 6. DLT will be defined as any of the events listed in this section that are at least possibly related to panobinostat that occur during the dose-finding period regardless of expectedness. The dose-finding period is defined as the first course of therapy in both strata.

Management and dose modifications for toxicities which occur outside of the dose-finding period should also follow Section 6; however, these will not be considered dose limiting for the purpose of dose escalation.

5.1.4 Definitions of Dose-Limiting Toxicities (DLTs):

Patients who miss more than 2 doses due to toxicity will be considered to have experienced a DLT.

5.1.4.1 Non-hematologic dose limiting toxicity is defined as:

- Any Grade 3 or greater non-hematologic toxicities with the specific exclusion of the following:
 - o Grade 3 nausea/vomiting that is responsive to antiemetics, and that resolves to \leq Grade 2 within 5 days
 - o Grade 3 electrolyte abnormality that resolves to \leq Grade 2 within 5 days
 - o Grade 3 rash that is not considered medically significant or intolerable by the

- patient
 - Grade 3 diarrhea that resolves to \leq Grade 1 with optimal use of anti-diarrheal medication
 - Grade 3 fever that resolves to \leq Grade 2 within 5 days
 - Grade 3 infection that resolves to \leq Grade 2 within 5 days
- Any Grade 2 non-hematological toxicity that persists for more than 7 days and is considered sufficiently medically significant or sufficiently intolerable by patients as to warrant treatment interruption and/or dose reduction will be considered dose limiting.
- Any panobinostat-related non-hematological toxicity that results in a delay of treatment $>$ 14 days between treatment courses

5.1.4.2 *Hematologic dose limiting toxicity is defined as:*

- Grade 4 thrombocytopenia (platelet count $<$ 25,000/ μ L)
- Grade 3 thrombocytopenia with bleeding
- Grade 3 thrombocytopenia (platelet count \geq 25,000 but $<$ 50,000/ μ L) that occurs twice within a treatment course will be considered a DLT. (Note: platelet transfusions are recommended for platelet counts $<$ 50,000/ μ L and transfusion should target platelet corrections to $>$ 100,000 / μ L)
- Myelosuppression that causes greater than a 14-day delay between treatment courses
- Grade 4 neutropenia
- Grade 3 or 4 febrile neutropenia

5.1.4.3 *Follow-up for toxicities:*

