and Timetable for Submission form located on the PBTC-047 Protocol webpage for the schedule. For assistance, contact the PBTC Protocol Coordinator listed on the cover page. An optional roadmap is located on the PBTC-047 Protocol Webpage.

5.3.2 *Off Treatment Criteria*

At the discontinuation of treatment, the “Off Treatment Date” is to be recorded in the eCRF and is to be consistent with the reason given for going off treatment. The “Last Treatment Date” is defined as the last date that the patient received protocol based therapy. Date of “off treatment” must be the greatest of the date of last treatment, date of procedure, date of patient assessment, notification of patient/family decision, or decision made by the physician that resulted in the patient being taken off protocol treatment. The reason for discontinuation of treatment must be documented by the attending investigator in the medical record and recorded in the eCRF.

Patients will be considered Off Treatment for the following reasons:

- Development of unacceptable toxicity as outlined in Section 5.1.3. See Section 7 for specific adverse event reporting requirements.
- Progressive disease (PD) as described in Section 11.2.4.
- Development of a medical or psychiatric illness or social issue that in the investigator's judgment renders the patient incapable of further therapy on this protocol or the treating physician determines continuation on this study is not in the patient's best interest.
- The patient, parent or legal guardian refuses further treatment on this protocol. In this case the investigator should clarify if the family also wishes to withdraw consent for continued participation for data collection purposes.
- Completion of all protocol defined treatment
- Pregnancy
- Non-compliance that in the opinion of the investigator does not allow for ongoing participation.

Patients who are off protocol therapy must be followed until an “Off Study Criterion” is met.

5.3.3 *Data Submission Schedule for Patients Off-Treatment*

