If a patient experiences dose-limiting hematological toxicity as outlined in Section 5.1.4.2 (i.e. grade 4 thrombocytopenia [$< 25 \times 10^9/L$] or grade 3 thrombocytopenia [< 50 and $\geq 25 \times 10^9/L$] with bleeding, or grade 3 twice within 1 treatment cycle or grade 4, or grade 3 or 4 febrile neutropenia) treatment will be withheld. Platelets should be transfused to a count of $> 100 \times 10^9/L$ (i.e. a post-transfusion platelet count should be obtained). Counts should then be checked every 3-4 days (and when medically indicated) during this time.

If the toxicity resolves to meet on study parameters within 14 days of drug discontinuation, provided there is no current active bleeding in the case of dose-limiting thrombocytopenia, the patient may resume therapy at one dose level lower. Patients who are dose-reduced for toxicity will not have their dose re-escalated.

If toxicity does not resolve to meet on study parameters within 14 days of drug discontinuation, the patient must be removed from protocol therapy.

Only one dose-reduction per patient is allowed. If any dose-limiting toxicity occurs in a patient already dose-reduced for toxicity, the patient must be removed from protocol therapy.

Table 13

Criteria for dosing delays, dose-reductions, and re-initiation of treatment due to study drug-related non-hematological toxicity (excluding QT prolongation)

Worst Toxicity CTCAE Grade* unless otherwise specified (Value)		Dose Modification Guidelines At any time during a course of therapy (including intended day of dosing) Note: If dose limiting toxicity does not resolve after holding drug for 14 days, patient will be removed from treatment
NON-HEMATOLOGICAL TOXICITIES		
CARDIAC		
Cardiac - Prolonged QT interval**		Please refer to Section 6.3.
GASTROINTESTINAL		
Diarrhea	Grade 2 (4-6 stools/day over baseline, etc.) despite the use of optimal antidiarrheal medications	None. If unacceptable to patient or medically concerning, then hold until recovery to \leq grade 1, or baseline, up to 14 days, then restart original schedule at unchanged dose level
	Grade 3 (\geq 7 stools/day over baseline, etc.) despite the use of optimal antidiarrheal medications	Temporarily discontinue panobinostat dosing until resolved to \leq grade 1, or baseline, then restart original schedule reduced by one dose level
	Grade 4 (life-threatening consequences, hemodynamic collapse, etc.) despite the use of optimal antidiarrheal medications	Discontinue panobinostat dosing

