Brain MRI with diffusion ^B	X		After every 2 courses for the first 6 courses, then after every 3 courses until progression	End of Tx or progression	Every 3 months until progression
Spinal MRI (if clinically indicated) ^{B,C}	X		After every 2 courses for the first 6 courses, then after every 3 courses until progression	End of Tx or progression	Every 3 months until progression

^A This should also be done whenever clinically indicated.
^B All required imaging dates are to be entered in the database. However, only scans showing a partial response or complete response, and that same subject's baseline scan, will be uploaded.
^C MRI Spine should be done at the indicated time and when clinically indicated. If no disease is present within the spine at baseline, spine MRIs will be obtained as clinically indicated and at the discretion of the primary treating physician.

Table 19

Correlative Laboratory Studies	Pre-therapy	Course 1	Course 2, 4, 6, 12
Tumor Tissue and Blood for Biorepository (optional)	X		
Pharmacokinetics Plasma (required)		
 Day 1: pre-dose and at 0.5, 1, 2, 4, 8 (± 1), and 24 (± 4) hours after the oral dose. Day 3 (2nd dose): single sample will be collected prior to the dose 	
Pharmacodynamics: Cell-free DNA – Blood (optional)		Day 1, Courses 1, 2, 4, 6, 12, prior to drug dose (Optional Biorepository: Leftover Sample Storage for Future Research)	
Pharmacodynamics: Cell-free DNA – Urine (optional)		Day 1, Courses 1, 2, 4, 6, 12, prior to drug dose, preferably in morning (No longer collected as of version 8.0)	

11 Measurement of Effect

Although the clinical benefit of panobinostat has not yet been established, the intent of offering this treatment is to provide a possible therapeutic benefit, and thus the patient will be carefully monitored for tumor response and symptom relief in addition to safety and tolerability. Patients with measurable disease will be assessed by standard criteria. For the purposes of this study, patients should be re-evaluated by MRI after every 2 courses for the first 6 courses, then every 3 courses and when clinically indicated until disease progression or off-study criteria are met.

11.1 *Definitions*

11.1.1 *Evaluable for Toxicity*

Patients who receive at least 1 dose of the study regimen and are removed from treatment for toxicity during the first course (dose-finding period) are evaluable for estimating the MTD.

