Patients who receive approximately 83-85% of prescribed therapy (i.e. $\geq 8/9$ doses in stratum 1 and $\geq 5/6$ doses in stratum 2) during the dose-finding period but who progress prior to completing the course may be considered evaluable for estimating the MTD, as long as no additional anti-cancer therapy or supportive care that would confound the interpretation of any observed toxicity or side effect is given. Patients must have completed all of the clinical and laboratory monitoring requirements specified by the protocol up to the time of disease progression for them to be considered evaluable for MTD estimation.

Patients who receive less than 83-85% of the protocol specified therapy (i.e. miss >1 dose) and who go off treatment for reasons other than toxicity (e.g., progressive disease, withdrawal of consent etc.) during the dose finding period will be considered inevaluable for estimating the MTD and may be replaced.

Patients who complete all therapy during the dose-finding period but who fail to comply with all the specified clinical and laboratory monitoring requirements for the first course may be considered inevaluable for estimating the MTD and may be replaced.

11.1.2 *Evaluable for Radiographic Response*

Only those patients who have measurable disease present at baseline, have received at least one course of therapy, and have had their disease re-evaluated will be considered evaluable for response. These patients will have their response classified according to the definitions stated below. (Note: Patients who exhibit objective disease progression prior to the first scheduled MRI will also be considered evaluable.)

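### Section 11.1.1 has no exception for a patient who already had a DLT, so a DLT patient who misses more than 1 dose and then leaves course 1 for progression or withdrawal is inevaluable for the MTD

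*Combined protocol and SAP*

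**What the plan says.** Section 11.1.1 gives one route to evaluability through toxicity. Patients who receive at least 1 dose and "are removed from treatment for toxicity during the first course (dose-finding period) are evaluable for estimating the MTD". Having a DLT is not itself a criterion.

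A later paragraph of 11.1.1 covers patients below the dose cut-off (more than 1 dose missed) "who go off treatment for reasons other than toxicity (e.g., progressive disease, withdrawal of consent etc". It says that such patients "during the dose finding period will be considered inevaluable for estimating the MTD and may be replaced". The verb is mandatory, and no DLT exception is given. The paragraph on incomplete monitoring has no DLT exception either. Section 13.1.2 names an incomplete course as an example of a ground for inevaluability, again without one.

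Other sections treat the event as data:
- Section 5.1.3 defines a DLT as a listed event, at least possibly related, in the dose-finding period. It sets no condition on doses received or on the reason for leaving. Only for toxicities outside that period does it say that "these will not be considered dose limiting for the purpose of dose escalation".
- Section 5.1.4 adds: "Patients who miss more than 2 doses due to toxicity will be considered to have experienced a DLT".
- Section 6.2 withholds drug after a hematologic DLT. If the toxicity resolves within 14 days, "the patient may resume therapy at one dose level lower".
- Section 2.4 shows this in use: one Stratum 1 patient had "grade 4 thrombocytopenia and grade 4 neutropenia, and was dose reduced to level 1".

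**The concern.** Two sections give different answers for the same patient. Sections 5.1.3 and 5.1.4 record a DLT. Section 11.1.1 removes the patient from the data that estimate the MTD and allows a replacement.

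DLT outcomes are the only toxicity input to the CRM, and counts per level are small. Compared with a rule that keeps every DLT, a dropped one lowers the observed rate.

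The rule is still live. Under the version 8 update in Section 13.2, Stratum 2 level 3 has been declared too toxic, 6 patients have been treated at level 2, and up to 70 − 47 = 23 more may enrol, with allowance for inevaluable patients. Section 13.1.2 continues at the lower dose until 12 have been treated and the model does not suggest de-escalation. The open question is whether level 2 holds or the trial moves to level 1.

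**Working it through.** **1. The cut-off.** Section 11.1.1 states at least 8/9 doses (Stratum 1) or 5/6 (Stratum 2). Missing 1 dose leaves 8/9 = 88.9% or 5/6 = 83.3%, which meets it. Missing 2 leaves 7/9 = 77.8% or 4/6 = 66.7%, which does not. A hold that costs 2 doses is therefore enough in either stratum.

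**2. The route can occur.**
- Stratum 2, doses on days 1, 3, 5, 15, 17, 19: a DLT is found on day 15, doses 4 and 5 are held, and the family withdraws on day 18 with 3/6 doses taken. The 14-day limit has not passed, whether counted from the last dose (5 + 14 = day 19) or from the hold (15 + 14 = day 29).
- Stratum 1, doses on days 1, 3, 5, 8, 10, 12, 15, 17, 19: a DLT is found on day 8, doses 4 to 6 are held, doses 7 to 9 are given one level lower, and the patient leaves for progression on day 25 with 6/9 doses. The 3 missed doses are themselves a DLT under 5.1.4.

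Both patients are inevaluable under 11.1.1.

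**3. Effect on the CRM.** Inputs from Section 13.1.2: target 0.25 and Stratum 2 skeleton s = 0.05, 0.13, 0.25, 0.40, 0.54 for levels 0 to 4. Model: p_i = s_i^β, with β by maximum likelihood; choose the level with p_i nearest 0.25. All patient counts are assumed, because the documents give no Stratum 2 DLT counts. Level 1 is 0/3 throughout.

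| Level 2 | Level 3 | Fitted rates | Nearest level |
|---|---|---|---|
| 2/6 (DLT kept) | none | L2 0.251, L3 0.401 | 2 |
| 1/5 (DLT dropped) | none | L2 0.151, L3 0.286 | 3 |
| 2/7 (kept) | none | L2 0.225, L3 0.373 | 2 |
| 1/6 (dropped, DLT-free replacement) | none | L2 0.132, L3 0.263 | 3 |
| 5/12 (kept) | 5/12 | L1 0.184, L2 0.317 | 1 |
| 4/11 (dropped) | 5/12 | L1 0.160, L2 0.288 | 2 |

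The fifth row is close: the distances from 0.25 are 0.066 for level 1 and 0.067 for level 2. With level 3 at 4/12 instead, both 5/12 and 4/11 stay at level 2.

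**4. Effect on the 33% restrictions, if they use evaluable patients only.** 3/9 = 33.3% closes level 2 to new patients. Dropping one DLT gives 2/8 = 25.0%, and a DLT-free replacement then gives 2/9 = 22.2%. Both leave it open.

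**5. Average effect, on the same evaluable-only reading.** Let p be the true DLT rate, d the loss among DLT patients and c the loss among the others. The observed rate is q = p(1−d) / [p(1−d) + (1−p)(1−c)]. Take p = 0.33 and add patients one at a time from 7 to 12, closing the level when DLTs/n ≥ 0.33 (CRM ignored). The loss rates and starting counts are assumed.

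| d / c | q | Closed, start 1/6 | Closed, start 0/6 |
|---|---|---|---|
| 0 / 0 | 33.0% | 37.9% | 10.8% |
| 10% / 0 | 30.7% | 33.4% | 8.6% |
| 10% / 10% | 33.0% | 37.9% | 10.8% |
| 5% / 10% | 34.2% | 40.3% | 12.0% |

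**The case against.** **The 33% restrictions may not be touched.** Section 11.1.1 removes a patient only from MTD estimation, while the restrictions speak of patients treated who have experienced a DLT. Read plainly, 3/9 stays 3/9 and level 2 closes as before. A reader might infer that one lost DLT reopens level 2, but the documents do not establish this. The same reading limits step 3. At 2/6 = 33.3%, the restriction would block level 3 whatever the model says. At 5/12 = 41.7% or 4/11 = 36.4%, level 2 is closed to new patients either way, and only the model's verdict on de-escalation differs. The 2/7 against 1/6 pair does not depend on the restrictions, because 2/7 = 28.6% is below 33%. It describes escalation to level 3, however, which is now past.

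**The 12-patient point.** A reader might set 4/12 against 3/11 as a changed decision. The stated test at 12 is the model, and it stays at level 2 for both (level 3 assumed at 4/12 or 5/12).

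**The trigger is narrow.** It needs a DLT, at least 2 missed doses and an exit for another reason, all within course 1. If toxicity does not resolve in 14 days, 6.2 requires removal, and the patient is then evaluable. Section 5.3.2 also lists "Development of unacceptable toxicity as outlined in Section 5.1.3" as a reason to stop. If that governed every DLT, the gap would close, but 6.2 allows resumption, and Section 2.4 shows patients continuing at a reduced dose.

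**Practice looks sound.** Both dose-reduced patients in Section 2.4 were counted as DLTs. The one recorded early progression is not said to have followed a DLT. The clause was probably meant for under-exposed patients without a DLT.

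These objections limit the consequence. They do not supply the missing exception.

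**Conclusion.** The point stands as a wrong written rule with a limited consequence, and it should be clarified. As written, 11.1.1 discards from MTD estimation a DLT that 5.1.3 and 5.1.4 count.

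The direct effect is on the CRM input. One dropped DLT can change the level that the model names, under assumed counts and in some cases by a thin margin. An effect on the 33% restrictions is conditional on the evaluable-only reading.

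The average effect is small: on that reading, losing 10% of DLT patients and no others lowers the chance of closing level 2 from 37.9% to 33.4% (start 1/6) or from 10.8% to 8.6% (start 0/6). It would be tempting to say that the rule biases the MTD upward. The documents do not support that, because they give no loss rates. Equal loss gives no bias, and heavier loss among patients without a DLT pushes the rate the other way. Nor do they show that any DLT has been lost.

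**What to change.** Add to 11.1.1, ahead of the exclusion paragraphs, that any patient who receives at least 1 dose and has a DLT in the dose-finding period is evaluable for MTD estimation, whatever the doses received, the monitoring compliance or the later reason for leaving. Limit the inevaluability paragraphs to patients without a DLT. State in 13.1.2 that the 33% restrictions count every such DLT. Re-check the patients already classed as inevaluable at Stratum 2 levels 1 and 2.

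Separately, 5.3.2 and 6.2 must be reconciled. Which clinical rule applies is for the study team to state.

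The cost is a few sentences and a check of a few records. The statistical downside is a slight upward, conservative bias, because early leavers without a DLT are still dropped. With p = 0.25 and all DLTs kept, the observed rate is 0.25 / [0.25 + 0.75(1−c)], which is 26.0% at an assumed c = 5% and 27.0% at c = 10%.

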11.2 Tumor Response Criteria

11.2.1 Complete Response (CR)

Complete disappearance on MR of all evaluable tumor and mass effect, on a stable or decreasing dose of corticosteroids (or receiving only adrenal replacement doses), accompanied by a stable or improving neurologic examination. If CSF was positive, it must be negative.

11.2.2 Partial Response (PR)

Greater than or equal to 50% reduction in tumor size by bi-dimensional measurement, as compared with the baseline measurements, on a stable or decreasing dose of corticosteroids, accompanied by a stable or improving neurologic examination. *Axial FLAIR images will be used for tumor measurements.*

11.2.3 Stable Disease (SD)

Neurologic exam is at least stable and maintenance corticosteroid dose not increased, and MR/CT imaging meets neither the criteria for PR nor the criteria for Progressive Disease

11.2.4 Progressive Disease (PD)

Progressive Disease (PD): Progressive neurologic abnormalities or worsening neurologic status not explained by causes unrelated to tumor progression (e.g., anticonvulsant or corticosteroid toxicity wean, electrolyte disturbances, sepsis, hyperglycemia, etc.), OR a greater than 25% increase in the bi-dimensional measurement, taking as a reference the smallest disease measurement recorded since the start of protocol therapy, OR the appearance of a new tumor lesion.

Increasing doses of corticosteroids required to maintain stable neurological status should be strongly considered as a sign of clinical progression unless in the context of recent wean or transient neurologic change due e.g. to radiation effects.

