2.5.2 Rationale for Pharmacodynamic Studies

2.5.2.1 Cell-free DNA in peripheral blood or urine

Several tumor suppressor genes associated with the malignant phenotype are repressed by epigenetic mechanisms in sporadic cancers. Thus, therapy with DAC inhibitors may alter tumor phenotype and inhibit growth in such tumors. In collaboration with [name], who has established a method to detect H3K27 in serum and urine, we will prospectively evaluate this method and evaluate potential changes after treatment with panobinostat.

3 Patient Selection

All subjects must meet the following inclusion and exclusion criteria. No exceptions will be given. Imaging studies to establish eligibility must be done within two weeks, prior to enrollment. Clinical evaluations to establish eligibility must be done within 7 days prior to enrollment.

3.1 ***INCLUSION CRITERIA FOR CHILDREN WITH RECURRENT/ PROGRESSIVE DIPG (Stratum 1)***

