3.1.1 Diagnosis

Patients with progressive DIPG, as defined by progressive neurologic abnormalities or worsening neurologic status not explained by causes unrelated to tumor progression (e.g., anticonvulsant or corticosteroid toxicity wean, electrolyte disturbances, sepsis, hyperglycemia, etc.), OR an increase in the bi-dimensional measurement, taking as a reference the smallest disease measurement recorded since diagnosis, OR the appearance of a new tumor lesion since diagnosis.

- Please note: patients with a radiographically typical DIPG, defined as a tumor with a pontine epicenter and diffuse involvement of more than 2/3 of the pons, are eligible without histologic confirmation.
- Patients with pontine lesions that do not meet these radiographic criteria will be eligible if there is histologic confirmation of malignant glioma WHO II-IV.

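### Read literally, the size criterion for PD in Section 11.2.4 leaves the pre-treatment MRI out of its reference, so growth up to the first scheduled on-treatment scan does not count as PD by size

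*Combined protocol and SAP*

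**What the plan says.** Section 11.2.4 gives three alternative routes to PD:

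- clinical: "Progressive neurologic abnormalities or worsening neurologic status not explained by causes unrelated to tumor progression";
- size: "OR a greater than 25% increase in the bi-dimensional measurement", "taking as a reference the smallest disease measurement recorded since the start of protocol therapy";
- new disease: "OR the appearance of a new tumor lesion".

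The other size rules name their own anchors. PR in Section 11.2.2 is a reduction of at least 50% "as compared with the baseline measurements". Stratum 1 eligibility in Section 3.1.1 looks for an increase "taking as a reference the smallest disease measurement recorded since diagnosis".

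On timing, Section 3 says "Imaging studies to establish eligibility must be done within two weeks, prior to enrollment", Section 3.6 requires treatment to start within 7 days of enrollment, and Section 9.4 places the baseline MRI before therapy. After that, under Section 11, "patients should be re-evaluated by MRI after every 2 courses for the first 6 courses", then every 3 courses, with further scans as clinical need arises. A course is 28 days.

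PD feeds several other rules. SD (Section 11.2.3) is imaging that is neither PR nor PD, with a stable neurologic exam and no steroid increase. Starting another course requires disease that is stable or better (Section 5.1.2). PFS ends at documented PD or death (Sections 11.2.5 and 13.3.3). The off-treatment list in Section 5.3.2 cites Section 11.2.4.

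**The concern.** A scan taken before the first dose is not, in ordinary words, a measurement recorded since therapy began. If it is left out, the first on-treatment scan has nothing earlier to be compared with, and the size route cannot operate at that visit. A neurologically stable child whose tumour has grown well beyond 25% since baseline, with no new lesion and no steroid increase, would then be SD as written.

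Three things are at stake: the date of PD and hence PFS, a secondary objective in both strata; the split between SD and PD; and consistency between sites, since some readers will add baseline without comment and others will follow the text. Central review cannot be relied on to remove such differences. Section 9.4.3 sets out specific confirmation only for PR and CR. Section 9.4 and the calendar footnote limit uploads to response scans and their baselines, while Section 9.4.2 describes transfer at every time point.

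**Working it through.** The plan states no figure on this point, so there is none to reproduce. The check is arithmetic on the rule under two readings. The growth percentages are illustrative assumptions, not trial data.

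**Inputs.** PD threshold: more than 25% (Section 11.2.4). Course length: 28 days (Section 5.1.2). Scheduled MRI after every 2 courses at first (Section 11). Eligibility imaging up to 14 days before enrollment (Section 3). First dose up to 7 days after enrollment (Section 3.6).

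**Timing, with no delays between courses.**
- First scheduled on-treatment MRI: 2 × 28 = day 56.
- Second: 4 × 28 = day 112.
- Longest lead of the baseline scan over the first dose, taking the eligibility scan as baseline: 14 + 7 = 21 days.
- Longest interval over which growth is uncounted on the literal reading: 21 + 56 = 77 days.

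**Two readings of the reference.** Set baseline at 1 and the first scheduled scan at 1 + g, with no unscheduled scan in between.
- Literal: reference at the first scan = 1 + g. Change = (1 + g)/(1 + g) − 1 = 0% for any g. PD by size at the second scan then needs more than 1.25 × (1 + g) − 1 over baseline, if the first scan is the smallest on treatment.
- Inclusive: reference = the smaller of 1 and 1 + g. For g > 0 the change is g, and PD by size follows if g > 25%.

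| Growth at first scan (g) | Literal change | Inclusive change | Growth over baseline needed at second scan, literal |
|---|---|---|---|
| 26% | 0% | 26% (PD) | > 57.5% |
| 30% | 0% | 30% (PD) | > 62.5% |
| 50% | 0% | 50% (PD) | > 87.5% |
| 100% | 0% | 100% (PD) | > 150% |

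**Effect past the first scan.** Growth of 60% by day 56 and a further 20% by day 112 gives 1.60 × 1.20 = 1.92, or 92% over baseline. The step between the two on-treatment scans is 20%, so on the literal reading this is still not PD by size at day 112.

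**Where the readings agree.** If the tumour first shrinks, say 10 to 8 and then to 10.5, the reference is 8 either way and the increase is (10.5 − 8)/8 = 31.25%. The readings part only when baseline is smaller than every later reference scan.

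**Side by side with Section 11.1.2.** That section counts patients with objective progression before the first scheduled MRI as evaluable for response. By size, with no earlier on-treatment scan, such progression can be shown only against the pre-treatment scan. The literal wording of Section 11.2.4 does not allow that comparison.

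**The case against.** The strongest reply is that the literal reading defeats the rule. An increase presupposes an earlier measurement. The pre-treatment MRI is mandatory, and the protocol schedules a scan after course 2 precisely to judge whether disease is stable. A sensible radiologist would include baseline. Section 11.1.2 points the same way, and the eligibility wording in Section 3.1.1 uses a parallel phrase that most naturally includes the measurement at diagnosis. The contrast with PR proves little, because PR is measured from baseline alone and PD from a minimum.

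This is a good argument about intent, and it is probably right. It does not remove the problem: no sentence says baseline is included, and a new lesion would also satisfy the note in Section 11.1.2, so that note does not settle the reading. If intent and wording differ, the wording needs correcting.

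Other parts of the reply stand and limit the point. A reader might infer that early progression cannot be called PD at all. The documents do not support that: neurologic decline and new lesions remain open at any time, and a rising steroid need is to be strongly considered as clinical progression. A reader might also infer a fixed move of the earliest size-based PD from about week 8 to about week 16. That holds for scheduled scans only, because an unscheduled on-treatment scan can set an earlier reference, although growth from baseline to that scan would still go uncounted. Finally, nothing shows how sites have applied the rule, so upward bias in PFS is a risk where the text is followed, not an established fact.

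**Conclusion.** The point holds as a defect of wording with a definite consequence when the wording is followed. At the first scheduled on-treatment MRI, about day 56, growth from baseline contributes nothing to the size criterion unless an earlier unscheduled on-treatment scan exists. For a patient with 30% growth at that scan and no other sign of progression, PD by size comes no earlier than the next scan, about day 112 on schedule, and only if growth then exceeds 62.5% over baseline. Where sites read it this way, PD can be recorded as SD and PFS can be biased upward. The overall size cannot be given, because it depends on growth rates and site practice that the documents do not report.

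The reach is limited. PFS is descriptive and reported by stratum, with no test or threshold resting on it. The DLT/CRM dose finding uses course 1 only and is untouched, as is the sample size. A reader might conclude that the protocol keeps patients on treatment past progression. The documents support only a narrower statement: Section 5.3.2 inherits the ambiguity by citing Section 11.2.4, and the passages must be reconciled.

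**What to change.** For response classification and PFS, state in Section 11.2.4 that the reference for the size increase is the smallest measurement on study, including the pre-treatment baseline scan.

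Ask the sponsor to reconcile Sections 11.2.4, 11.1.2 (progression before the first scheduled MRI) and 11.2.2 (PR against baseline), and the off-treatment criterion in Section 5.3.2 that cites Section 11.2.4. How the treatment rule should read is for the sponsor and is not proposed here.

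The cost is one phrase in the endpoint definition. It needs no new scans, because the baseline MRI is already required.
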